There is a new alternative that combines the most commonly used antibiotic and anti-inflammatories into a single drop. The use of a single drop compounded ophthalmic solution may offer advantages such as increased compliance, patient comfort and reduced ocular toxicity. Three combinations are available today: Pred-Gati, Prednisolone acetate and gatifloxacin hydrochloride; Pred-Nepaf, Prednisolone acetate and nepafenac; and Pred-Gati-Nepaf, Prednisolone acetate, gatifloxacin hydrochloride, and nepafenac. Different studies have shown the safety and efficacy of topical antibiotic/steroid combination with comparable results to standard single component topical medication used prophylactically pre and post cataract surgery.²⁵⁻²⁸ Additionally, in a recent study, Pred-Moxi-Ketor used three times a day for one week followed by Pred-Ketor twice a day for 2 – 4 weeks was compared to an intravitreal injection containing triamcinolone, moxifloxacin and vancomycin (Tri-Moxi-Vanc). Results showed similar outcomes with good control of postoperative inflammation and patient comfort without any unexpected adverse events.²⁹

The purpose of this study is to evaluate the efficacy of Pred-Gati-Brom and compare it to the standard topical drops regimen used for routine cataract surgery.

1. OBJECTIVE:

To assess the efficacy of a formulation containing prednisolone acetate, gatifloxacin hydrochloride, and bromfenac used as combination drop therapy before and after routine cataract surgery and intraocular (IOL) implantation compared to standard prophylactic treatment that includes the topical use of Gatifloxacin, Bromfenac, and Prednisolone acetate 1%.

2. STUDY DESIGN AND METHODS:

2.1. Assessed article: Formulation containing prednisolone acetate, gatifloxacin hydrochloride, and bromfenac.

2.2. Study Design: Prospective, randomized, single site, contralateral eye study.

2.3. Subjects:

2.3.1. Inclusion Criteria:

Subjects **MUST** fulfill the following conditions to qualify for enrollment into the trial

1. Subject is undergoing bilateral cataract extraction or refractive lens exchange with intraocular lens implantation.
2. Gender: both males and females.
3. Age: 50 years and older.
4. Willing and able to provide written informed consent for participation in the study.
5. Willing and able to comply with scheduled visits and other study procedures.
6. Willing and able to administer eye drops and record the times the drops were instilled.

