5. STATISTICAL CONSIDERATIONS

5.1. Sample size

We estimate that the ability of the Cirrus OCT to measure changes in macular thickness has a standard deviation around 6 microns. For sample size calculation we set the statistical significance to $\alpha = 0.05$ with a power (beta) of 0.9. Using a dependent model, detecting a 5 micron difference in the change in retinal thickness between eyes is estimated to require 30 subjects. To allow for 15% dropout, 35 subjects will be enrolled.

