5.2. Statistical Analysis

All data will be collected by the site and entered into a database. Subjects will be assigned an ID number. Data analysis will be performed without patient identification. Statistical analysis will be performed using standard descriptive statistics and other tests as deemed appropriate based on the characteristics of the data to be analyzed. All statistical tests will be two-sided and interpreted at a 5% significance level. Comparisons between the groups will be made. Data analysis will be conducted by a third party consultant.

5.3. Study Endpoints:

Comparisons between the groups:

5.3.1. Primary Endpoints:

- Change from baseline (preoperative exam) in macular thickness at Days 15 \pm 2 and 30 \pm 5.

5.3.2. Secondary Endpoints:

- The change from baseline in corneal thickness at Day 1, Day15 \pm 2, and Day 30 \pm 3.
- Slit lamp (cornea exam) changes at all times points.
- The proportion of subjects reporting no eye pain/discomfort (“0” on the eye pain/discomfort) at all time points.
- The change from baseline in eye pain/discomfort score at all time points.
- The proportion of subjects reporting FBS (“0”) at all time points.
- The change from baseline in FBS at all time points.
- The proportion of subjects reporting burning/stinging (“0”) at all time points.
- The change from baseline in burning/stinging at all time points.
- The proportion of subjects with a corneal pachymetry change from baseline at all time points.
- The change from baseline in corneal pachymetry measurements at all time points.
- The proportion of subjects with patient satisfaction score of 3 or higher at Day 30 visit.

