Appendix 1: Symptoms and Pain Questionnaire

1. Have you experienced foreign body sensation?

Yes No If yes, OD OS OU

If yes, did it start immediately after drop instillation?

OD: Yes No Don't remember

OS: Yes No Don't remember

How long did it last?

OD: 1 min or less 2 to 5 min 6-10 min > 10 min

OS: 1 min or less 2 to 5 min 6-10 min > 10 min

How severe was it?

OD: Mild Moderate Severe

OS: Mild Moderate Severe

Place a vertical mark on the line below to indicate the severity.

OD

No pain | _____ | Very Severe Pain

OS

No pain | _____ | Very Severe Pain

2. Have you experienced stinging/burning?

Yes No If yes, OD OS OU

If yes, did it start immediately after drop instillation?

OD: Yes No Don't remember

OS: Yes No Don't remember

How long did it last?

- OD: 1 min or less 2 to 5 min 6-10 min > 10 min
- OS: 1 min or less 2 to 5 min 6-10 min > 10 min

How severe was it?

- OD: Mild Moderate Severe
- OS: Mild Moderate Severe

Place a vertical mark on the line below to indicate the severity.

OD

No pain | _____ | Very Severe Pain

OS

No pain | _____ | Very Severe Pain

3. Have you experienced any pain/discomfort?

- Yes No If yes, OD OS OU

If yes, did it start immediately after drop instillation?

- OD: Yes No Don't remember
- OS: Yes No Don't remember

How long did it last?

- OD: 1 min or less 2 to 5 min 6-10 min > 10 min
- OS: 1 min or less 2 to 5 min 6-10 min > 10 min

How severe was it?

- OD: Mild Moderate Severe
- OS: Mild Moderate Severe

Place a vertical mark on the line below to indicate the severity.

OD

No pain | _____ | Very Severe Pain

OS

No pain | _____ | Very Severe Pain

4. Overall, how satisfied have you been with the results of your cataract surgery in your ...?

OD

OS

Very dissatisfied

Very dissatisfied

Dissatisfied

Dissatisfied

Neither satisfied nor dissatisfied

Neither satisfied nor dissatisfied

Satisfied

Satisfied

Very satisfied

Very satisfied

5. Given your postoperative vision/outcome, if you had to do it all over again, would you select:

LessDrops

3-Drops

6. Given your postoperative experience, if you had to do it all over again, would you select:

LessDrops

3-Drops

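### The five-level, per-eye satisfaction item is specified only as the proportion scoring 3 or higher at Day 30; a paired comparison of the full scale would use far more of the data

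*Combined protocol and SAP*

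**What the plan says.** The design is a "Prospective, randomized, single site, contralateral eye study", so each patient contributes a test eye and a control eye. Question 4 of the symptoms and pain questionnaire (Appendix 1) asks, separately for the right and left eye, "Overall, how satisfied have you been with the results of your cataract surgery in your" followed by a blank for the eye. Each eye has five ordered verbal answers from very dissatisfied to very satisfied, and the third is "Neither satisfied nor dissatisfied". No numbers are printed beside the answers. Appendix 1, item 8, has questions 4 to 6 asked only at Day 30.

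Section 5.3.2 uses this item once: "The proportion of subjects with patient satisfaction score of 3 or higher at Day 30 visit". Other measures in the same list have a proportion and also a full-scale version, for example "The change from baseline in eye pain/discomfort score at all time points" and "The change from baseline in FBS at all time points". Burning/stinging and pachymetry follow the same pattern.

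Section 5.2 names no test for satisfaction and leaves the choice to the character of the data. It adds: "All statistical tests will be two-sided and interpreted at a 5% significance level". Section 5.1 sizes the trial on macular thickness alone: "detecting a 5 micron difference in the change in retinal thickness between eyes is estimated to require 30 subjects".

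**The concern.** A paired comparison of proportions learns only from patients whose two eyes fall on opposite sides of the cut. Where the cut lies depends on a coding that the documents do not give. With 1-5 coding, a score of 3 is the neutral answer, so neutral eyes count as successes. With 0-4 coding, a score of 3 is *satisfied*. In both cases *satisfied* and *very satisfied* are on the same side, and that is plausibly where two eyes with uncomplicated surgery would differ.

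If most eyes are rated satisfied or better, both proportions sit near 100% and few pairs are informative. A finding of no difference in satisfaction could then reflect the cut and not the patients' answers. The five-level answers needed to avoid this are already being collected.

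**Working it through.** **Number of pairs.** Section 5.1 gives a 5 micron difference, SD 6 microns, alpha 0.05 and power 0.9. The formula n = 2(1.960 + 1.282)² × 6²/5² = 2 × 10.51 × 1.44 gives about 30.3, close to the stated 30. (It treats 6 microns as the SD for each eye with no correlation between eyes.) That figure concerns macular thickness; here it only fixes about 30 evaluable pairs.

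**What an exact paired test of proportions needs.** The plan names no test; exact McNemar is used here as the usual choice. With k discordant pairs all in one direction, the two-sided p is 2 × 0.5^k. For k = 5 this is 0.0625, and for k = 6 it is 0.031. So at least 6 one-directional pairs are needed, which is 6/30 = 20% of patients.

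**Assumed control-eye distributions** (percent, very dissatisfied to very satisfied; none is in the documents):
- High: 1/2/5/32/60
- Moderate: 3/5/12/40/40
- Low: 5/10/20/40/25

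**Hand check.** If the test eye is better, a pair can favour it only when the control eye is below the cut. The expected number of such control eyes among 30 is therefore a ceiling on the expected number of favourable pairs.

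| Distribution | Below third level | Below fourth level |
|---|---|---|
| High | 3% × 30 = 0.9 | 8% × 30 = 2.4 |
| Moderate | 8% × 30 = 2.4 | 20% × 30 = 6.0 |
| Low | 15% × 30 = 4.5 | 35% × 30 = 10.5 |

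At the third-level cut all three ceilings are below 6. At the fourth-level cut only the low-satisfaction case is clearly above it.

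**Simulation.** 30 pairs, bivariate normal latent scores cut at the assumed thresholds, fellow-eye correlation 0.5-0.7, test eye better by 0.6 latent SD, two-sided 5%, 3,000 trials per scenario:

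| Distribution | McNemar, third level and above (1-5 coding) | McNemar, fourth level and above (0-4 coding) | Signed-rank, five levels |
|---|---|---|---|
| High | 0% | 1-2% | 48-57% |
| Moderate | about 1% | 17-18% | 67-80% |
| Low | 8-9% | 35-40% | 75-88% |

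Repeat runs agree within about two points. Taking them together, the ranges are about 0-10%, 1-42% and 46-88%.

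**Sensitivity.**
- At 0.4 SD, the smallest gain of the full scale over either of these two cuts is about 24 points.
- If the test eye is worse by 0.6 SD, the two cuts reach 2-38% and 18-56%, against 65-93% for the signed-rank test.
- A separate set of distributions, with 60%, 35% and 20% of control eyes very satisfied, was run at correlation 0.5 and shift 0.5 SD. The third-level cut gives 0.1%, 2% and 17%, the fourth-level cut 2%, 13% and 30%, and the signed-rank test 44%, 57% and 64%.
- With no true difference, the signed-rank test rejected in about 2-5% of trials, so the gain is not bought with type I error.

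**The case against.** A reader might infer that 30 pairs give almost no power wherever the scale is cut. That is not supported. A cut at *very satisfied* reaches about 41-58% under the same assumptions (a repeat run gave 39-54%). Against that cut the signed-rank gain is only about 10-12 points in the high distribution, 17-25 in the moderate and 33-37 in the low. With a mid-p McNemar test, the top-level cut in the high distribution (51-58%) matches the signed-rank test (49-57%). Mid-range proportions also help: 70% against 40% gives 55-92% power over correlations of 0-0.7. This part of the objection stands, but a top-level cut is not what a score of 3 or higher means under either coding.

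Other points against:

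- **The six-pair minimum is not a property of the plan.** It belongs to exact McNemar. With mid-p, five one-directional pairs give p = 0.031; with the uncorrected test, four give chi-square 4 and p = 0.046. This stands.
- **The missing companion endpoint is not clearly an inconsistency.** The companions in section 5.3.2 are mostly changes from baseline, and satisfaction with the surgical result has no baseline. This stands, although a between-eye score comparison could still have been listed.
- **Section 5.2 leaves tests open.** A full-scale analysis is therefore not excluded. But the listed endpoint is itself a dichotomy, and a full-scale analysis chosen after seeing the data would be post hoc.
- **Preference is also collected directly.** Questions 5 and 6 ask which regimen the patient would choose again, so it would be wrong to infer that a real preference must go unrecorded. They are not listed endpoints.
- **The effect may be small.** Question 4 asks about the result of surgery, not the drops, and both regimens contain the same three drug classes. At a 0.2 SD shift the signed-rank test itself has only 8-17% power.

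**Conclusion.** The point holds as a cheap improvement to a secondary endpoint. The stated cut discards most of the information in a five-level paired item. At a 0.6 SD advantage for the test eye, power is about 0-10% if scores run 1-5 and 1-42% if they run 0-4, against about 46-88% for the full scale. The loss is greatest when satisfaction is high and smaller when it is low or the effect is large.

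These figures rest on assumed distributions, correlations and shifts, and on exact McNemar as the comparator. The direction is firmer than the size: the full scale beat both readings of the stated cut in every scenario run. The documents do not support going further, to a claim that the comparison fails at any cut or that the trial's main conclusion is at risk. The primary analysis is unaffected and the plan sets no power target for satisfaction.

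**What to change.** In section 5.3.2, replace the satisfaction bullet with wording such as: within-subject difference between test and control eye in the five-level question 4 score at Day 30, compared by an exact Wilcoxon signed-rank test. State the numeric coding of the five answers. Keep the proportion at the chosen cut as a descriptive summary only, reported with the five-by-five table of paired answers.

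This costs one line of wording. The item is already collected for each eye, so no new data, visits or patients are needed. The small downside is that a rank-based result is less simple to quote than a percentage; the descriptive proportion covers that.

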5.4. Safety Analyses

The type, severity, duration and frequency of reported ocular adverse events will be tabulated for each group. Adverse events will also be summarized for events that were

considered treatment-related. Comparison of treatment groups with respect to the proportion of study patients reporting adverse events will be made using Fisher's Exact Test.

6. DATA HANDLING AND RECORD KEEPING

6.1. Confidentiality

To ensure confidentiality in this study, records of the participants will be examined only by the principal investigator and research staff involved in the study. Study records will be kept on file at each site. Any statistical analysis and publication will not include any subject identifiers. Medical records will be made available only for review by the investigators, study Monitor or Auditor, Sponsor Company or Research Institution, the IRB, and other State or Federal Regulatory Agencies, if necessary. All information in these records will be kept confidential.

6.2. Records Retention

The PI is accountable for the integrity, retention and security of all study related data. The investigator must maintain accurate, complete and current records relating to the clinical study. The investigator must maintain the required records during the investigation and for a period of 1 year after the date on which the investigation is terminated or completed.

7. STUDY MONITORING, AUDITING, AND INSPECTING

7.1.1. The nature and location of all source documents will be identified to ensure that original data required to complete the case report forms (CRFs) exist and are accessible for verification by the monitor. If electronic source records are maintained, these records must be 21 CFR Part 11 compliant and will be printed and certified for verification by the monitor as needed.

7.1.2. Required examination must be recorded on the CRFs. CRFs can be used as source document. All data reported must have corresponding entries in the source documents. The principal investigator or sub-investigator must review the reported data and certify that the CRFs are accurate and complete. No subject identifiers should be recorded on the CRFs beyond subject number, subject initials and study specific identifiers.

7.1.3. Data from CRFs will be entered into a database. Database access is limited to study personnel and it is saved in the server.

7.1.4. Upon completion of the CRFs, the data will be reviewed and statistician for accuracy and completeness. If corrections and/or any additions to the data are deemed necessary, queries will be generated. Designated research staff expected to respond to data queries in a timely manner and ensure that the corrections and changes made to the data in the database are reflected in the subjects' source documentation. Any changes will need to be initialed and dated by the authorized personnel making such changes.

7.1.5. Data will not be sold to third parties nor will it be used for future research.

7.1.6. Electronic data will be stored and accessed on a portable device. However, the file is saved in the server that can be only accessed using a VPN private connection.

8. INVESTIGATIONAL PRODUCT

8.1. Description

The Symphony Toric IOL (ZXTx) is an extended depth of focus (EDOF) IOL design to improve the sharpness of vision at near, intermediate and far distances reducing the need of glasses after cataract surgery in patients with astigmatism. The EDOF IOL, similarly to a monofocal IOL, has one focal point, it is elongated in the EDOF, having less of a halo and glare problem compared to multifocal IOLs.

8.2. Treatment/Dosing Regimen

The Symphony Toric IOL (ZXTx) is intended for primary implantation for the visual correction of aphakia secondary to removal of a cataractous lens in adult patients. The IOL will be implanted at time of uncomplicated routine cataract surgery. Intraocular lenses are implantable medical devices and are intended for long term use over the lifetime of the patient.

8.3. Method for Assigning Subjects to Treatment/Dosing Groups

The statistician will provide randomization envelopes. The envelopes will be sequentially numbered and they will be provided to each site.

8.4. Subject Compliance Monitoring

Since the IOL is implanted at time of cataract surgery, subject compliance will not be an issue in this particular study.

8.5. Packaging, Receiving, Storage, Dispensing and Return

An account will be set up with the manufacturer of the lens (Abbott Medical Optics - AMO) that will provide the lens at no cost to the participants. IOLs will be ordered once the subjects qualification for the study has been confirmed. IOLs will be shipped to the site or ambulatory surgery center and will be stored and dispensed following the routine standard of care for cataract surgery. Unused IOLs will be returned to AMO following their instructions.

9. ETHICAL CONSIDERATIONS

This clinical trial will be conducted in accordance with the principles of the Declaration of Helsinki, and Good clinical practice. The Investigator and all clinical trial staff will conduct the clinical trial in compliance with this protocol. The Investigator will ensure that all personnel involved in the conduct of the clinical trial are qualified to perform their assigned duties through relevant education, training, and experience. Deviations from the clinical protocol must be documented in each subject's study records including the dates and reasons for each deviation. The PI must ensure that all aspects of the trial are in compliance with the applicable regulatory laws and conditions of approval imposed by the IRB.

10. IN CASE OF AN INJURY RELATED TO THIS RESEARCH STUDY

Every effort to prevent study-related injury will be taken by the study doctor and staff. In the event a patient is injured as a direct result of the study while following the study instructions and requirements, the patient will be instructed to immediately contact the principal investigator and/or study staff. Treatment will be provided as needed for those injuries caused directly by this research study. In the event of injury or illness caused by or occurring during the participation in this study, all charges for medical care provided will be billed to the patient's insurance company. The medical care costs for injuries or illnesses that are not caused directly by the research study will not be covered.

11. CONFIDENTIALITY/PUBLICATION OF THE STUDY

The existence of this Study is confidential and should not be discussed with persons outside of the Study. Results will be submitted for publication and presentation at national and/or international meetings. A manuscript will be submitted to peer-review journals for publication but there is no guarantee of acceptance.

Appendix 1: Standard Evaluation Procedures.

1. Uncorrected and Best-corrected Visual Acuity: To be evaluated preoperatively, at days 1, 15 and 30.

Visual acuity will be measured before tonometry or any other test that would affect vision. Visual acuity is measured using the ETDRS chart 1 at 4 m. If the subject cannot read at least 4 letters on the 20/200 line then the chart or the patient need to be moved to 1 meter and visual acuity recorded.

a. ETDRS technique:

- i. Testing starts with right eye; therefore, left eye is occluded.
- ii. The patient is seated and his/her back should firmly touch the back of the chair. The examiner should ensure that the patient is sitting comfortably, that the head does not move forward or backward during testing, and that the patient's eyes remain at the same distance.
- iii. The patient should be told that the chart has letters only and no numbers. If the patient forgets the instructions and reads a number, he or she should be reminded that the chart does not have numbers and the examiner should request a letter instead of a number.
- iv. The patient should be asked to read slowly (at a rate not faster than about one letter per second) in order to achieve the best identification of each letter and to not proceed until the patient has given a definite response. If the patient loses his or her place in reading or the examiner loses his or her place, the examiner should ask the patient to go back to the line where the place was lost. Examiners should not point to the chart or to specific letters on the chart or read any of the letters during the test. When the patient says he/she cannot read a letter, he/she should be encouraged to guess. If the patient identifies a letter as one of two or more letters, he/she should be asked to choose one letter. When it becomes evident that no further meaningful readings can be made, the examiner should stop the test for that eye. Each letter is scored as right or wrong. Once a patient has identified a letter with a definite single-letter response and has read the next letter, a correction of the previous letter cannot be accepted. If the patient changes a response aloud (e.g. "That was a "C," not an "O") before he or she has read aloud the next letter, then the change should be accepted. If the patient

changes a response after beginning to read the next letter, the change is not accepted.

- v. Ask the patient to read the smallest line that he/she could comfortably read. If patient misses one letter, ask the patient to read the line before and continue from there until patient misses 3 or more letters in a single line.
- vi. After the test of the right eye is completed, occlude the right eye. The test is repeated for the left eye following the same instructions.

b. ETDRS visual acuity scoring

- i. The examiner records letters read incorrectly and letters for which the patient makes no guesses with an "x".
- ii. The examiner underlines the last line on which the patient read any letter.
- iii. Each letter read incorrectly is scored as one point. The total number of missed letters is multiply by 0.02 to this result, the last line that the patient read correctly added and the log MAR score calculated and recorded on the source document for that visit

2. Manifest Refraction: will be done with a plus cylinder phoropter or trial lenses and the ETDRS chart R using the "Push plus" refraction technique. If refracting at 1 m, add a +0.75 D sphere lens to compensate for the closer distance.

1. Sphere

a. Plus (lowest line read)	Clearer No Change Blurrier	Increase plus. Increase plus STOP
b. Minus (lowest line read)	Clearer No Change Blurrier	Increase minus if additional letter(s) read. STOP STOP
c. Plus (lowest line read)	Clearer No Change Blurrier	Increase plus. Increase plus. STOP

2. Cylinder

a. Axis (C or O above lowest line read)	Clearer at 1 or 2	Move axis toward preferred plus axis until position 1 and 2 are equal.
--	-------------------	--

3. Cylinder

a. Power	Clearer at 1 or 2	Increase or decrease plus power until
----------	-------------------	---------------------------------------

(C or O on or above lowest line read)

neither position 1 or 2 is better. If power changes by ≥ 0.50 adjust sphere.

(Not present)

JCC at 90/180
JCC at 45/135

Place 0.25 D cylinder at preferred axis. Then, check cylinder axis and power as above.

4. Refine sphere Refine with +/- spheres as in step #1 until no improvement in vision.

3. **Corneal Edema:** Postoperatively at day 1, 15 and 30, corneal edema evaluation will be divided in stromal edema/folds and epithelial edema and it will be measured before tonometry or any other test that would affect examination. Both will be graded by the examiner using the following scale:

0 - no edema
1 - trace (0% - 5%)
2 - mild (5% - 25%)
3 - moderate (26% - 50%)
4 - severe (>50%)

4. **Anterior Chamber Cells and Flare:** Postoperatively at day 1, 15 and 30, anterior chamber cells and flare will be evaluated before tonometry or any other test that would affect examination. Both will be graded by the examiner using the following scale:

Number of Cells	Flare
0- none	0- none
1 - 1-5 cells	1 - Tyndall effect barely discernible
2 - 6-15	2 - mild Tyndall effect
3 - 16-30	3 - strong Tyndall effect
4- > 30	4 - intense Tyndall effect - aqueous has milky white appearance

5. **Macular thickness** (preop, days 15 and 30): It will be measured before tonometry or any other test that would affect OCT measurements. Macular thickness will be performed using SD-OCT (Cirrus [Zeiss]) following the manufacturer's recommendations. One 512 x 128 Macular Cube scan will be acquired per eye.
6. **Central corneal ultrasound pachymetry:** To be measured preop, and at day 1, 15 and 30. Three measurements will be taken and recorded as well as the average of the 3 measurements taken.

- 7. Intraocular pressure measurements:** IOP measurements will be measured at the Screening visit and at day 1, 15 and 30 postoperatively using Goldmann tonometry.
- 8. Questionnaires:** Examiner will read aloud the questions to the subject and will record the response given by the subject in the source document. For the Visual Analog Scale (VAS), the examiner will ask the patient to place a vertical mark on the line for each question then use ruler (cm) to calculate the score with 1 mm equal to 0.1 cm. A decimal value should be recorded (i.e., 2.1, 4.0). Questions 4 to 6 will be asked only at the Day 30 visit.
- 9. Dilated fundus examination:** To be performed preoperatively and at Day 30 (if deemed necessary by the investigator) using the investigator's preferred technique.

